#### 8.3.7 Pre-specification of Statistical Analysis

The primary outcome measure has been pre-specified as well as the type of statistical analysis to be performed to evaluate procedure success rate so as to minimize reporting bias. The precision analysis planned for the study, which includes construction of confidence intervals for the outcome summaries and a pre-defined range in which the 95% CI for the primary outcome are expected to fall within are designed to maximize the validity of the study results.

More detailed information on analyses to be carried out will be incorporated in the Statistical Analysis Plan (SAP) so as minimize any threats to external validity in order to yield clinically relevant estimates of effects and precision.

This document contains information that is confidential and proprietary to Smith + Nephew PLC and Smith + Nephew, Inc. and is intended for use only by Smith + Nephew and its manufacturer. It shall not be reproduced or copied in whole or in part, nor shall the contents be disclosed by any means without prior written permission from Smith + Nephew, nor shall anyone make any use of it that is contrary to the expressed or implied wishes of Smith + Nephew.

Study Protocol	% smith&nephew	
A prospective, multi-center, single arm PMCF study to evaluate the safety and performance of ENTACT™ (Next Generation) resorbable septal staple system for septoplasty	Number: ENTACT.ENT.PRO.SEP.2019.05	
	Version: 2.0, 27Aug2020	
	Page: Page 46 of 94	

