## 10. STATISTICAL DESIGN

A Statistical Analysis Plan (SAP) will be written and finalized prior to database lock. The SAP will contain more specific details of the statistical analyses that will be carried out as well as provide information on any changes or deviations from the projected analyses in this protocol. The

This document contains information that is confidential and proprietary to Smith + Nephew PLC and Smith + Nephew, Inc. and is intended for use only by Smith + Nephew and its manufacturer. It shall not be reproduced or copied in whole or in part, nor shall the contents be disclosed by any means without prior written permission from Smith + Nephew, nor shall anyone make any use of it that is contrary to the expressed or implied wishes of Smith + Nephew.

Study Protocol	> ∕ smith&nephew
A prospective, multi-center, single arm PMCF study to evaluate the safety and performance of ENTACT ™ (Next Generation) resorbable septal staple system for septoplasty	Number: ENTACT.ENT.PRO.SEP.2019.05
	Version: 2.0, 27Aug2020
	Page: Page 54 of 94

Clinical Study Report (CSR) will also highlight changes made to the analyses specified in the protocol.

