## 10.1 General

Smith+Nephew's Global Biostatistics group or designee will conduct the statistical analysis for this study. Unless otherwise stated, all significance tests will be two-sided, performed at the 5% significance level. Resulting p-values will be quoted. Point estimates and their corresponding 95% two-sided confidence intervals will be generated where appropriate. Where data summaries are specified, categorical and ordinal variables will be summarized with frequencies and percentages. Continuous variables will be summarized with the following summary statistics: number of observations, mean, median, standard deviation, minimum, and maximum values. All analyses will be performed in SAS 9.4 (or later).

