## 10.3 BASELINE DATA

Data to be summarized at baseline includes but is not limited to all collected demographic variable such as age, gender, primary diagnosis, height, weight, Body-Mass-Index and medical history. The baseline variables will be used to describe the outcome data where necessary.

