### 10.4 EFFICACY ANALYSIS

## **10.4.1 Analysis of Primary Endpoint**

Data will be collected on whether the septum wall appearance and need for re-intervention at the surgery site are due to the device or the procedure. Only those that are device-related will contribute to the primary endpoint analyses, in line with the primary objective of this study. A binary variable will be defined as follows; one if all five of the following criteria are true and 0 if at least one of the criteria is false:

- Septum wall straight appearance
- Complete coaptation of perichondrial flaps on septum wall
- Absence of significant local tissue reaction at the staple site
- Absence of hematoma swelling at the staple site
- No need for re-intervention at the surgery site

Clinical success will be inferred for a patient if their binary variable is 1. Clinical success will be reported as a count and percentage with a 95% CI using Clopper-Pearson Exact methodology. A logistic model will be used to evaluate the adjusted and unadjusted models for the primary outcome variable. The variables considered important and to be included in the final model are age and BMI. All other baseline and medical factors collected at baseline will be evaluated for

This document contains information that is confidential and proprietary to Smith + Nephew PLC and Smith + Nephew, Inc. and is intended for use only by Smith + Nephew and its manufacturer. It shall not be reproduced or copied in whole or in part, nor shall the contents be disclosed by any means without prior written permission from Smith + Nephew, nor shall anyone make any use of it that is contrary to the expressed or implied wishes of Smith + Nephew.

Study Protocol	Smith&nephew
A prospective, multi-center, single arm PMCF study to evaluate the safety and performance of ENTACT ™ (Next Generation) resorbable septal staple system for septoplasty	Number: ENTACT.ENT.PRO.SEP.2019.05
	Version: 2.0, 27Aug2020
	Page: Page 56 of 94

importance in adjusted models and only those statistically significant in an unadjusted model will be considered in the final model.

This analysis will be carried out using the FAS as the primary analysis population and the PP population using for sensitivity analysis.

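### With about 3 expected failures, the logistic model and significance screen in section 10.4.1 cannot give interpretable covariate results

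*Combined protocol and SAP*

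**What the plan says.** Protocol section 10.4.1 defines a binary day-21 outcome: "one if all five of the following criteria are true and 0 if at least one of the criteria is false". Septum appearance and re-intervention are restricted further: "Only those that are device-related will contribute to the primary endpoint analyses". The outcome is reported as a count and percentage with an exact 95% interval.

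The same section then plans adjusted and unadjusted logistic models. Two terms are fixed: "The variables considered important and to be included in the final model are age and BMI". Every other baseline and medical factor is a candidate, and "only those statistically significant in an unadjusted model will be considered in the final model". The analysis is run in the FAS and, as sensitivity, in the PP population.

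Section 10.1 supplies the default threshold: "all significance tests will be two-sided, performed at the 5% significance level". Section 10.3 names "age, gender, primary diagnosis, height, weight, Body-Mass-Index and medical history" but says the list is not limited to these. Section 11 assumes at least 92% success, taken from one-week tissue fixation with an earlier device generation, with 36 evaluable and 40 enrolled subjects. Section 10 leaves detail to a later document: "The SAP will contain more specific details of the statistical analyses that will be carried out". It adds that the SAP will also report changes from the protocol's analyses.

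**The concern.** The information in a logistic model comes from the rarer outcome, here failures. Section 11 implies very few of them. Two separate problems follow.

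- **Sparsity.** The age and BMI odds ratios would be too imprecise to interpret, and the screen would miss even large effects.
- **Multiplicity.** An open-ended list is tested at 5% per factor with no control. With few failures, a factor that passes a likelihood-ratio screen often has an empty cell, and entering it leaves maximum likelihood without a finite estimate.

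These results would appear under the primary endpoint in a study meant to support CE marking. A factor that passes could be a chance finding. One that does not pass would not have been shown to be unimportant.

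**Working it through.** **Inputs from the protocol.** Success 92%, so failure rate q = 0.08; n = 36 evaluable, 40 enrolled (section 11; 36/0.90 = 40). Two forced slopes and an unadjusted screen (section 10.4.1), two-sided 5% (section 10.1). The plan gives no expected number of failures. Its precision figure does reproduce: at 92% and n = 36, the chance that a Wald 95% interval has half-width of at most 11 points is 84.3%, consistent with the stated minimum of 80%. So 92% and 36 are the right planning inputs.

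**Assumptions not in the documents.** Composite success of 85% or 96% as sensitivity values; 5 or 10 candidates; independence; binary prevalence of 10-50%; the effect sizes; age and BMI as independent standard normals.

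**Step 1: failures.** F ~ Bin(n, q), so E(F) = nq.
- n = 36: 36 × 0.08 = 2.88; P(F = 0) = 0.92^36 = 5.0%; P(F ≤ 2) = 44%.
- n = 40: 40 × 0.08 = 3.20; P(F = 0) = 0.92^40 = 3.6%; P(F ≤ 2) = 37%.
- Failures per forced slope: 2.88/2 = 1.4 and 3.20/2 = 1.6.

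**Step 2: model and screen power.** The age and BMI columns come from 3,000 simulated null trials per setting, with a linear-programming check for separation. Trials with no failures count as having no finite estimate. CI span is the upper limit divided by the lower, per SD. Power comes from exact enumeration of 2×2 tables for a binary factor with true odds ratio 5 for failure, holding the overall failure rate at q. The power ranges cover both n and all prevalences; other paired entries are n = 36 / n = 40.

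| Composite success | Expected failures | P(0 failures) | Age+BMI: no finite estimate | Median CI span | LR power | Wald power |
|---|---|---|---|---|---|---|
| 92% | 2.88 / 3.20 | 5.0% / 3.6% | 8.6% / 5.6% | 16.3 / 13.9 fold | 21-31% | 0.5-15% |
| 85% | 5.4 / 6.0 | 0.3% / 0.2% | 0.8% / 0.3% | 8.3 / 7.2 fold | 27-44% | 7-35% |
| 96% | 1.44 / 1.60 | 23% / 20% | 29.7% / 27.0% | 42.9 / 32.2 fold | 8-20% | at most 5.5% |

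A separate 4,000-trial run at 92% gave 8.5% / 6.1% and 16.9 / 14.0 fold. For a continuous factor with odds ratio 2 per SD at 92% (6,000 trials), power is 21% / 24% by LR and 7% / 11% by Wald.

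**Step 3: false selection at 92%.** Per null factor, LR selects in 3-7% of trials and Wald in 0.1-1.7%. For K independent binary candidates, P(at least one) = Σ_f P(f)[1 − (1 − a_f)^K], where a_f is the selection probability given f failures.

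| | K = 5 | K = 10 |
|---|---|---|
| Exact 5% tests, 1 − 0.95^K | 23% | 40% |
| LR screen | 15-28% | 26-45% |
| Wald screen | 0.5-8% | 1-16% |
| An LR-selected factor has an empty cell | 8-26% | 15-41% |

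The LR figures lie around the exact-test benchmark, so false selection is mainly ordinary multiplicity. The empty cells come from the few failures. At 85%, LR picks at least one null factor among 10 in 27-54% of trials, and an LR-selected factor has an empty cell in 12-40%.

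**Step 4: one case by hand.** Take 3 failures in 36 subjects and a factor split 18/18, with ℓ(x, n) = x ln(x/n) + (n − x) ln(1 − x/n). For a 3-versus-0 split, G = 2[ℓ(3,18) + ℓ(0,18) − ℓ(3,36)] = 2(−8.110 + 0 + 10.326) = 4.43, p = 0.035. The factor passes, yet its odds ratio has no finite estimate (Fisher p = 0.23). For a 2-versus-1 split, LR p = 0.54 and it does not pass. Here the factor passes the LR screen only when it cannot be estimated. A Wald test never passes it.

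**The case against.** The strongest reply is that little depends on this model. Section 8.3.7 rests the study on "construction of confidence intervals for the outcome summaries", no success criterion uses the logistic results, and the unwritten SAP may restrict or drop the screen. Section 10.4.1 also says only that significant factors will be considered, not that they must be entered. All of this is true and limits the weight of the point. But nothing in the documents removes the rule, and a SAP that follows the protocol inherits it. The choice of estimator, test and separation rule can properly wait for the SAP and is not criticised here.

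Second, an age and BMI model usually does fit. At 92% a finite estimate exists in about 91-94% of trials, and most of the rest have no failures at all: separation adds 8.6 − 5.0 = 3.6 points at n = 36 and 5.6 − 3.6 = 2.0 at n = 40. That stands: for the forced terms the defect is imprecision, not failure to fit.

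Third, the composite rate is unknown and could be lower. At 80% there would be 7.2 to 8.0 failures and at 75%, 9 to 10, which is still only 4.5 to 5 per forced slope. The device-related restriction works the other way, towards fewer failures.

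Fourth, the false-selection figures depend on the test and on assumed candidates. Height, weight and BMI are plainly not independent. That also stands: the multiplicity figures are illustrative. Low power under either test is the firmer ground.

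**Conclusion.** The concern holds and the change should be made, though it does not threaten the primary result. At 92% composite success the plan expects 2.9 to 3.2 failures. Age and BMI odds ratios per SD then carry intervals spanning about 14 to 17 fold, and the screen detects a binary odds ratio of 5 at most 31% of the time by LR and 15% by Wald. At an assumed 85% the spans are still 7 to 8 fold and power is at most 44%; at 96% everything is worse. Chance selection is a further risk, chiefly with a likelihood-ratio screen, and its size depends on the assumed number and independence of candidates.

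The failure counts follow directly from section 11 if its one-week 92% carries over to the five-item day-21 composite, for which the documents give no rate.

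**What to change.** In protocol section 10.4.1:

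- keep the count, percentage and Clopper-Pearson interval as the primary analysis;
- delete the sentence that screens other baseline factors by unadjusted significance;
- label any age and BMI logistic model exploratory and descriptive, and state that it is not fitted if there are no failures (a penalised fit such as Firth's is an option, not a requirement);
- list the baseline characteristics of each failure.

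Carry the same wording into the SAP. Keeping the screen but labelling the whole covariate analysis exploratory, with no inference from selected or unselected factors, would reduce the harm; deletion is cleaner. The cost is wording only: no added subjects, visits or data. What is lost is a data-driven search for other predictors, which so few failures cannot support.

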## 10.4.2 Analysis of Secondary Endpoints

Nasal cavity assessments at day 5 and day 42 will be summarized and presented as count and percentage of each criterion.

Successful staple deployment at the operative visit will be summarized by count and percentage. A 95% exact confidence interval for a single proportion will be presented for successful staple deployment using the Clopper-Pearson method. The number of staples used and whether the stapler misfired will also be presented.

Total operating room time will be calculated and summarized using descriptive statistics and will be presented descriptively by septoplasty only cases as well as septoplasty and turbinate reduction cases.

Intra-operative time to deploy staples to complete septoplasty, calculated as time between start of closure to when the stapler was handed back to the scrub nurse, will be summarized and presented descriptively by septoplasty only cases as well as septoplasty and turbinate reduction cases.

NOSE score will be calculated and summary statistics will be presented by visit. Change in NOSE score from the pre-operative visit to each post-operative visit will also be presented and an ANOVA model will be used to assess statistical significance.

This document contains information that is confidential and proprietary to Smith + Nephew PLC and Smith + Nephew, Inc. and is intended for use only by Smith + Nephew and its manufacturer. It shall not be reproduced or copied in whole or in part, nor shall the contents be disclosed by any means without prior written permission from Smith + Nephew, nor shall anyone make any use of it that is contrary to the expressed or implied wishes of Smith + Nephew.

Study Protocol	% smith&nephew
A prospective, multi-center, single arm PMCF study to evaluate the safety and performance of ENTACT™ (Next Generation) resorbable septal staple system for septoplasty	Number: ENTACT.ENT.PRO.SEP.2019.05
	Version: 2.0, 27Aug2020
	Page: Page 57 of 94

The VAS Pain score will be summarized by visit. Change in VAS Pain score from the preoperative visit to each post-operative visit will also be presented and an ANOVA model will be used to assess statistical significance.

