### 8.3 **STUDY ENDPOINTS**

#### 8.3.1 Primary Endpoint

At the 21-day follow-up visit, the clinician will examine the patient's nasal cavity and will confirm:

- Septum wall straight appearance (yes/no);
- Complete coaptation of perichondrial flaps on septum wall (yes/no);
- Absence of significant local tissue reaction at the staple site (yes/no);
- Absence of hematoma swelling at the staple site (yes/no);
- No need for re-intervention at the surgery site (yes/no);

If all the answers to the questions above are "YES" then clinical success will be inferred (if any answer is "NO" then repair failure will be inferred).

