## 8.3.3 Safety Endpoints

Following are the safety endpoints for this study:

- Device-related re-intervention;
- All adverse events (AEs) occurring from the time of surgery until re-intervention or study completion;
- Device related AEs (ADEs) and serious adverse events (SAE's);
- Device deficiencies (DDs)

All AEs will be categorized in terms of seriousness and relatedness to the study device or to the surgical procedure. All Serious Adverse Device Effects will be further categorized as Anticipated or Unanticipated. The definitions for each of these categories are based on ISO 14155:2011.

This document contains information that is confidential and proprietary to Smith + Nephew PLC and Smith + Nephew, Inc. and is intended for use only by Smith + Nephew and its manufacturer. It shall not be reproduced or copied in whole or in part, nor shall the contents be disclosed by any means without prior written permission from Smith + Nephew, nor shall anyone make any use of it that is contrary to the expressed or implied wishes of Smith + Nephew.

Study Protocol	> ∕ smith&nephew
A prospective, multi-center, single arm PMCF study to evaluate the safety and performance of ENTACT™ (Next Generation) resorbable septal staple system for septoplasty	Number: ENTACT.ENT.PRO.SEP.2019.05
	Version: 2.0, 27Aug2020
	Page: Page 45 of 94

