## 9.1.4 Follow-up Visit (Visit 4) Day 21 (± 7 days)

- 1. Query subject regarding any changes in general health and the use of concomitant medications.
- 2. Record assessment of nasal cavity.
- If any adverse device effects or device deficiencies are observed or reported, they must be recorded as instructed in Section 12, adverse events and device deficiencies. Also record concomitant medications/therapies used to treat AEs.
- 4. Complete NOSE score assessment and VAS pain score.
- 5. Instruct the subject on follow-up procedures, including returning the treatment facility at 42 days post-operative (± 7) days for follow-up visit.
- 6. If applicable, complete an End of Study CRF.

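### The protocol names no Day 21 table by criterion and no count of procedure-attributed findings, so the reasons behind the primary result cannot be read from the planned output

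*Combined protocol and SAP*

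**What the plan says.** Four places in the protocol bear on this.

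- **Section 8.3.1** defines the primary endpoint at Day 21 as five yes/no items on the nasal examination. Its rule is unconditional: "if any answer is 'NO' then repair failure will be inferred".
- **Section 10.4.1** codes the endpoint as "one if all five of the following criteria are true and 0 if at least one of the criteria is false". It also says that data will be collected on whether "septum wall appearance and need for re-intervention at the surgery site are due to the device or the procedure", and then: "Only those that are device-related will contribute to the primary endpoint analyses". The planned output is "Clinical success will be reported as a count and percentage with a 95% CI using Clopper-Pearson Exact methodology", plus logistic models of the same binary variable.
- **Section 10.4.2** covers the separate criteria: "Nasal cavity assessments at day 5 and day 42 will be summarized and presented as count and percentage of each criterion". Section 8.3.2 likewise lists the five items as secondary endpoints at Days 5 and 42 only.
- **Section 9.1.4** shows that the Day 21 examination takes place: "Record assessment of nasal cavity".

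On safety, Section 8.3.3 lists "Device-related re-intervention" as an endpoint, and Section 10.5 summarizes all safety endpoints and adverse events. Section 10 defers further detail to a SAP to be finalized before database lock. That SAP is not in the text supplied.

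**The concern.** The composite mixes different things. Flap coaptation is what the staple is for (Section 6.1.1). Tissue reaction and hematoma concern local safety. A septum that is not straight may reflect the operation rather than the device. With only the composite at the primary visit, a reader cannot tell which of these produced the failures, and no criterion can be followed across all three follow-up visits.

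The attribution filter adds to this. The cause is recorded for two of the five criteria and used to decide what counts, but no summary of it is planned. The study is open-label (Section 8.2.2). Section 8.4.3 gives the follow-up examinations to investigators not involved in the procedure, but the protocol does not say who judges cause. An unblinded judgment can therefore lift the reported success rate above what Section 8.3.1 would give, and no Day 21 output shows by how much.

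**Working it through.** **1. The plan's own figures.** Section 11 gives 92% assumed success, 36 evaluable subjects and 10% dropout.

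- Enrolment: 36 / (1 − 0.10) = 40, as stated.
- For X ~ Binomial(36, 0.92), the probability that a 95% Wald interval has half-width at most 0.11 is 84.3%. This agrees with the stated figure of at least 80%.
- Expected failures: 36 × (1 − 0.92) = 2.88, so 33/36 is a typical result under the plan's assumption.

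The point does not depend on the sample size. These figures only set a realistic scale.

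**2. Outputs named, by visit (Sections 10.4.1 and 10.4.2).**

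| Visit | Each criterion | Composite | Device/procedure split |
|---|---|---|---|
| Day 5 | count and percentage | none named | none named |
| Day 21 | none named | count, percentage, exact CI, logistic models; device-related filter | none named |
| Day 42 | count and percentage | none named | none named |

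**3. What the filter could conceal.** Assume 33/36 is reported under the device-related rule. Let k be the number of those 33 whose only NO was on septum appearance or re-intervention and was attributed to the procedure. Success regardless of cause (Section 8.3.1) is then (33 − k)/36. Intervals are Clopper-Pearson 95%.

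| k (assumed) | Success regardless of cause | 95% CI |
|---|---|---|
| 0 | 33/36 = 91.7% | 77.5% to 98.2% |
| 1 | 32/36 = 88.9% | 73.9% to 96.9% |
| 2 | 31/36 = 86.1% | 70.5% to 95.3% |
| 3 | 30/36 = 83.3% | 67.2% to 93.6% |

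This reads the filter as turning a procedure-attributed NO into a success. Section 10.4.1 could also mean that such subjects leave the denominator. With k = 3 that gives 30/33 = 90.9%, again above 83.3%. No Day 21 output named in the protocol reports k under either reading.

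**4. What the composite leaves open about coaptation.** If 33/36 succeed, the other three may all have failed coaptation or none may have. Day 21 coaptation could then be anywhere from 33/36 (91.7%, CI 77.5% to 98.2%) to 36/36 (100%, CI 90.3% to 100%).

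**The case against.** A reader might infer that the reasons for failure, and any procedure-attributed crooked septum, appear in no planned output at all. The documents do not support that.

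- Septum straightness is tabulated at Day 42 with no filter stated, so a deviation still present then is counted, though without its cause.
- Device-related re-intervention is a safety endpoint.
- Hematoma or inflammation reported as adverse events would be summarized and compared with the limits in Table 4.4.1-1.
- NOSE is summarized at Day 21.

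These outputs narrow the gap but do not close it. None links a finding to a Day 21 failure. The re-intervention endpoint carries the same device-related restriction. The notes to Table 9.1.1-1 end data collection after re-intervention on the implant, so a subject re-operated between Days 21 and 42 has no Day 42 examination.

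A reader might also infer that the filter hides a common poor surgical result. Nothing in the documents says how often that occurs, and every count above is assumed.

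Nor does the benchmark in Section 11 require Day 21 coaptation. It is fixation at one week, which fits Day 5 better, and coaptation is tabulated at Day 5.

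Two further objections stand in part. A display by component often belongs in the SAP, and the promised SAP may contain one. The omission also does not bias the estimate under whichever rule is adopted, and the Day 21 data could be tabulated later. But Section 8.3.7 relies on pre-specification to limit reporting bias, and the protocol already specifies this table for the other two visits.

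**Conclusion.** The concern holds in a limited form. The protocol names no Day 21 output that shows which criterion caused a primary failure, or how many NO answers attributed to the procedure were left out of the failures. Other planned outputs show these only in part. Sections 8.3.1 and 10.4.1 also give different rules for the primary endpoint, and the difference between them cannot be recovered from the named outputs.

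On the assumed counts, three filtered subjects would separate a reported 91.7% from 83.3% regardless of cause, a gap of 3/36 = 8.3 percentage points. The true size is unknown and may be zero. The conclusion covers the protocol only. It is a reporting change that should be made, not a flaw in the sample size or the interval method.

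**What to change.** - In Section 10.4.2, extend the by-criterion summary to Day 5, Day 21 and Day 42. For each criterion give number examined, count, percentage and exact 95% CI.
- At Day 21, show all-cause and device-related counts side by side for septum appearance and re-intervention.
- Report Day 21 composite success under both the any-NO rule of Section 8.3.1 and the device-related rule of Section 10.4.1. Reconcile the two sections on which is primary, and state whether a procedure-attributed NO counts as a success or leaves the denominator.
- Give the device/procedure split at Day 5 and Day 42 only if attribution is recorded there. The CRF is not supplied, and the protocol mentions attribution only for the primary endpoint.

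The cost is a few words in the protocol, a matching SAP entry and some table rows. It needs no extra subjects, visits or examinations, because Sections 9.1.4 and 10.4.1 already provide for the Day 21 assessment and attribution.
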